## **2.2. AMB-05X**

AMB-05X is an antagonistic fully human antibody (immunoglobulin G, type 2 [IgG2]) specific to the extracellular domain of human c-fms (CSF1R). It potently blocks both CSF1- and IL-34-mediated proliferation of growth factor-dependent human myelomonocytic cells in vitro and also effectively interacts with the monkey receptor but not other species such as rodents.

## **2.3. Summary of Nonclinical Data**

### **2.3.1. Pharmacology**

AMB-05X binds with high affinity to c-fms expressed on the surface of human myelomonocytic cells (AML-5 cells) and to cynomolgus monkey c-fms expressed on the surface of human embryonic kidney cells transformed by adenovirus (293E cells).

AMB-05X inhibits CSF1-induced phosphorylation of human c-fms. In addition, this antibody caused immunoprecipitation of human c-fms and its known single nucleotide polymorphism (SNP) variants. AMB-05X potently inhibits CSF1-driven proliferation of both human and cynomolgus monkey primary-bone-marrow-derived monocyte/macrophage cells in vitro as well as CSF1- and IL-34-driven proliferation of human myelomonocytic AML-5 cells.

AMB-05X does not cross-react with mouse c-fms. Therefore, a surrogate anti-mouse c-fms antibody, M279, was developed and tested for activity to be used in nonclinical tumor model studies in mice. This antibody, in an analogous manner to AMB-05X, potently and specifically inhibits c-fms-mediated activity in vitro. In vivo, M279 significantly inhibited the growth of a variety of xenograft and syngeneic tumor models, including MDA-MB-231 (human breast adenocarcinoma), Renca (mouse renal cell carcinoma, syngeneic), and NCI-H1650 and NCI-H1975 (human non-small-cell lung carcinomas) tumor models by 50% to 70% based on tumor volume. In addition, TAM content in all tumors treated with M279 compared with control-treated was shown to be significantly decreased by a variety of methods, including immunohistochemistry (IHC), flow cytometry, and immunofluorescence.

### 2.3.2. Pharmacokinetics

In cynomolgus monkeys, exposure to AMB-05X showed a nonlinear increase at single intravenous (IV) doses of 0.1 to 5 mg/kg but was approximately dose proportional in the dose range of 5 to 100 mg/kg. When the receptor-mediated clearance had been saturated at higher serum concentrations of AMB-05X [REDACTED] µg/mL), the kinetics of this protein became linear. The volume of distribution at steady state for AMB-05X in monkeys was approximately equal to plasma volume, indicating limited extravascular distribution.

Toxicokinetics (TK) of AMB-05X, as assessed in both the 4-week and 14-week repeat-dose toxicity studies, did not differ markedly between male and female monkeys. In general, exposure to AMB-05X increased approximately dose proportionally in monkeys over the dose range of 10 to 300 mg/kg. No marked (> 2-fold) accumulation of AMB-05X was observed after 4 or 13 once-weekly doses in monkeys. During the dosing phase of these studies, treatment-associated anti-AMB-05X-binding antibodies (ADAs) in monkeys administered AMB-05X were detected in 1 of 30 animals in the 4-week study and 13 of 35 animals in the 14-week study; during the recovery phase of the 14-week study, ADAs were detected in 8 of 10 animals. In general, ADAs decreased the exposure of AMB-05X in these animals. For both studies, high concentrations of AMB-05X in the serum samples may have interfered with detection of ADAs in animals that tested ADA-negative.

### 2.3.3. Toxicology

In the in vivo toxicology studies in the cynomolgus monkey, animals received up to 300 mg/kg, IV, weekly for 4 or 14 weeks. In the 4-week and in both 14-week studies, all direct AMB-05X-related findings were attributed to the expected pharmacology of inhibition of macrophages. Additionally, changes related to the acute post-dosing formation of ADA/drug complex (also called circulating immune complexes [CICs]) occurred in some animals on the 14-week study.

Clinical observations attributed to AMB-05X pharmacology consisted of reversible periorbital swelling due to increased extracellular matrix as observed by light microscopy. Clinical pathology changes included reversible increases in serum ALT, AST, and glutamate dehydrogenase (GLDH) without a light microscopic correlate in the liver and without elevations in sorbitol dehydrogenase (SDH), a liver-specific marker of injury. The increased extracellular matrix and elevated activities of serum enzymes are considered to result from decreased clearance due to inhibition of macrophages (Radi, 2011). Additional AMB-05X-related changes included decreased bone turnover, characterized by elongation of bone growth plates and decreased number of osteoclasts, and decreases in serum markers of bone turnover, both of which were reversible. The presence of yeast organisms in the lung and protozoal organisms in the gastrointestinal tract in a few animals (contributing to death in 1 animal) may be incidental or a pharmacologic effect of AMB-05X. Increased neutrophil counts occurred in association with myeloid hyperplasia.

During the last 2 months of the dosing phase in the 14-week study, acute post-dosing sequelae (platelet effects and clinical signs including death) were observed in ADA-positive animals at 10 and 50 mg/kg. The role of ADA/drug complexes in the acute post-dosing findings was confirmed by demonstration of ADA/drug complexes serologically and immunohistochemically. No post-dosing CICs or related effects occurred at 300 mg/kg. Retrospective analyses correlating

immunogenicity rates in animals and humans demonstrate low predictive value of nonclinical immunogenicity rates for human clinical responses (Ponce, 2009). Moreover, for nonclinical species dosed with human or humanized proteins, immunogenicity in animals is generally greater than in humans. For these reasons, the observed adverse effects in ADA-positive monkeys at 10 and 50 mg/kg attributed to the formation of ADA/drug complexes are not considered to be predictive of human clinical risk.

Synovial concentrations of AMB-05X can be extrapolated from the GLP cynomolgus monkey studies with repeat-administration AMB-820 (AMB-05X) for 14-weeks. In these studies, peak serum concentrations over the dosing period were █ mg/mL which would translate to █ µg/mL steady-state synovial fluid concentrations (Stepensky, 2012; AmMax modeling; AMB051-20-NHP1 study results).

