#### **2.3.5. Clinical Safety Extrapolation**

The projected human synovial fluid concentrations are projected to be █ µg/mL (█ nM) throughout a 2-week intra-articular dosing regimen of 150 mg (or greater). This synovial concentration is well above a projected effective concentration. From a systemic exposure perspective, as described above, intra-articular dosing of cynomolgus monkey knees at or above the clinical regimen appeared safe and well-tolerated. Importantly and as anticipated, serum

exposures remained very low - significantly below that associated with any transaminase elevations in Amgen's Phase 1/2 monotherapy study in patients with advanced solid tumors ([Papadopoulos, 2017](#)). As reported, no transaminase elevations or other AEs of concern were observed at an exposure of [REDACTED]  $\mu\text{g}\cdot\text{hr}/\text{mL}$  (1.5 mg/kg IV) and limited AST elevation or other AEs were observed at [REDACTED]  $\mu\text{g}\cdot\text{hr}/\text{mL}$  (3 mg/kg IV). Systemic exposures in the 14-week i.v. monkey GLP toxicology wherein findings through 300 mg/kg were related to exaggerated pharmacology far exceeded anticipated systemic exposures in the pending clinical trial. Thus, nonclinical and prior clinical study results support the 12-week intra-articular dosing trial as designed.

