### **6.5. Visit 5 (Week 6 ± 3 days)**

Complete the following procedures during the visit:

- Record any changes in concomitant medications since the previous visit.

- Record any AEs that may have occurred since the previous visit and follow up on the status of any existing AEs.
- Conduct a full physical exam and document any changes since the previous visit.
- Measure vital signs (blood pressure, heart rate, temperature, and respiratory rate) with the subject in a sitting position after having rested for 5 minutes.
- Obtain weight.
- Perform a 12-lead ECG.
- Collect a urine sample for urinalysis.
- Collect blood samples for clinical laboratory tests (chemistry and hematology).
- Collect synovial fluid for measurement of AMB-05X concentration and CSF1 levels prior to study drug injection.
- Perform MRI.
- Tumor assessment.
- Perform the following clinical assessments:
  - Worst stiffness NRS
  - PROMIS Physical Function Scale
  - BPI
  - EQ-5D-5L
  - Joint ROM
- Inject study drug.
- Observe subject for a minimum of 90 minutes after dosing to monitor for any adverse reactions, including any injection-site reactions.

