## 6.7. Visit 7 (Week 10 ± 3 days)

- Record any changes in concomitant medications since the previous visit.
- Record any AEs that may have occurred since the previous visit and follow up on the status of any existing AEs.
- Measure vital signs (blood pressure, heart rate, temperature, and respiratory rate) with the subject in a sitting position after having rested for 5 minutes.
- Obtain weight.
- Collect serum samples prior to dosing for measurement of AMB-05X concentration and CSF1 levels.
- Collect synovial fluid for measurement of AMB-05X concentration, CSF1 levels, and anti-AMB-05X antibodies prior to study drug injection.
- Inject study drug.
- Observe subject for a minimum of 90 minutes after dosing to monitor for any adverse reactions, including any injection-site reactions.
- Collect serum samples 2 hours post-dosing for measurement of AMB-05X concentration and CSF1 levels.

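### The exposure margin in Section 2.3.5 does not cover the immune-complex events seen at 10 and 50 mg/kg, and no blood count is clearly scheduled within a week after any injection

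*Combined protocol and SAP*

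**What the plan says.** Section 2.3.3 describes two classes of finding in the monkey studies. The direct findings are put down to macrophage inhibition. Separately, "changes related to the acute post-dosing formation of ADA/drug complex (also called circulating immune complexes [CICs]) occurred in some animals on the 14-week study". The second class is then specified: in the last two months of dosing, "acute post-dosing sequelae (platelet effects and clinical signs including death) were observed in ADA-positive animals at 10 and 50 mg/kg". For the top dose, "No post-dosing CICs or related effects occurred at 300 mg/kg". The section closes by saying that the adverse effects "attributed to the formation of ADA/drug complexes are not considered to be predictive of human clinical risk", because animal immunogenicity rates predict human rates poorly.

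Section 2.3.5 summarizes the same 14-week work in one clause: "findings through 300 mg/kg were related to exaggerated pharmacology far exceeded anticipated systemic exposures in the pending clinical trial". It does not mention the immune-complex events.

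On measurement, the Schedule of Events (Section 1.3) places hematology at Screening, Baseline and Weeks 6, 12 and 24. The Week 6 list (Section 6.5) includes "Collect blood samples for clinical laboratory tests (chemistry and hematology" ahead of the injection. The only blood draws scheduled after an injection on a dosing day are at Weeks 0 and 10. For Week 10, Section 6.7 says: "Collect serum samples 2 hours post-dosing for measurement of AMB-05X concentration and CSF1 levels". Neither draw includes a blood count.

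Sections 1.3, 4.1 and 9.4 call for a serum ADA sample before the Week 10 dose. The Week 10 visit list in Section 6.7 names serum samples only for drug and CSF1.

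**The concern.** A safety margin argued from a high animal dose works when harm rises with exposure. The immune-complex events did not: they appeared at the two lower doses and not at the highest. The statement in Section 2.3.5 therefore leaves out the one finding to which its logic does not apply, and that finding included death.

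The dismissal in Section 2.3.3 concerns how often humans form antibodies, not what happens to a subject who does. The clinical summaries in Section 2.4.1 give no human ADA rate. Section 2.3.4 reports very low exposure in 2 of 4 monkeys after a second joint injection, possibly due to ADA and still under investigation, so the question is open for the trial's own route.

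Frequency and severity of treatment-emergent adverse events is the primary endpoint, and the data monitoring committee and sponsor use the safety data in decisions on dose. If counts come only long after each injection, an absence of observed platelet change may partly reflect when blood was taken.

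**Working it through.** The plan gives no figure to reproduce here: about 12 subjects are planned, without power or precision inputs. The check is a comparison of the dose levels and of the visit days.

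**1. How far each animal dose lies from the trial dose.** Section 2.3.4 equates 1.5 mg/kg with about 100 mg and about 2.5 mg/kg with about 160 mg. The implied body weights are 100/1.5 = 66.7 kg and 160/2.5 = 64 kg. The starting dose of 150 mg is then 150/66.7 = 2.25 mg/kg or 150/64 = 2.34 mg/kg.

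| Animal dose | Immune-complex events | Ratio to 150 mg |
|---|---|---|
| 10 mg/kg | yes | 10/2.34 to 10/2.25 = 4.3 to 4.4 |
| 50 mg/kg | yes | 50/2.34 to 50/2.25 = 21.3 to 22.2 |
| 300 mg/kg | none | 300/2.34 to 300/2.25 = 128 to 133 |

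Against 210 mg the 10 mg/kg ratio is 3.0 to 3.2, and against 90 mg it is 7.1 to 7.4. These are dose ratios only. The exposures are redacted, and the monkeys were dosed intravenously every week while the trial doses into the joint every two weeks, so the ratios are not exposure margins.

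**2. How common ADA was in monkeys (Section 2.3.2).** 1/30 = 3.3% in the 4-week study, 13/35 = 37.1% during dosing in the 14-week study, and 8/10 = 80% in its recovery phase. The same section warns that high drug levels may have hidden ADA in animals that tested negative.

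**3. Time from each injection to the next scheduled count.** Days and windows come from Section 1.3. The shortest gap is (count day − window) − (injection day + window); the longest is (count day + window) − (injection day − window). The Week 6 count is taken as pre-injection.

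| Injection | Next count | Nominal gap (days) | Range with windows |
|---|---|---|---|
| Week 0, Day 1 | Week 6, Day 43 ± 3 | 42 | 39 to 45 |
| Week 2, Day 15 ± 2 | Week 6 | 28 | 23 to 33 |
| Week 4, Day 29 ± 2 | Week 6 | 14 | 40 − 31 = 9 to 46 − 27 = 19 |
| Week 6, Day 43 ± 3 | Week 12, Day 85 ± 3 | 42 | 36 to 48 |
| Week 8, Day 57 ± 3 | Week 12 | 28 | 22 to 34 |
| Week 10, Day 71 ± 3 | Week 12 | 14 | 82 − 74 = 8 to 88 − 68 = 20 |

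Three counts are scheduled after dosing starts. None falls sooner than 8 days after an injection, and only the Week 4 and Week 10 injections have a count by about the end of their own two-week interval.

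**4. What the added counts would give.** Two tubes for 12 subjects make 2 × 12 = 24; an optional 2-hour tube at Week 0 makes 3 × 12 = 36. If all 12 subjects reach Week 10 and none shows a fall, the one-sided 95% upper limit for the event rate is 1 − 0.05^(1/12) = 22.1%. The counts describe; they do not exclude a rare event.

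**The case against.** Section 2.3.5 never says in terms that its margin covers the immune-complex events, and Section 2.3.3 deals with them on separate grounds. Nor does Section 2.3.5 rest on the 14-week study alone: it also cites tolerability of joint injection in monkeys and serum exposures below those linked to transaminase elevations in humans. This stands, so the problem is best called an omission that leaves the margin statement too broad.

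Section 2.4.1.2 reports no clinically relevant hematology trends in the two parts of the combination study (15 and 101 subjects), and Section 2.3.4 reports no abnormal behavior in daily observation. This is reassuring but not decisive. Mean treatment was 0.8 and 1.6 months, the timing of those counts relative to infusions is not given, and the Section 2.3.4 summary mentions no blood counts.

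A reader might infer three stronger things that the documents do not support:

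- That no blood count follows any injection and the event would go unmeasured. Counts are drawn at Weeks 6, 12 and 24, and those who stop before Visit 8 have the Week 12/ET tests, at a time not tied to the last injection. Subjects are observed for at least 90 minutes after each dose, and adverse events are recorded at every visit.
- That deaths occurred only at the two lower doses. Section 2.3.3 reports organisms in a few animals, "contributing to death in 1 animal) may be incidental or a pharmacologic effect of AMB-05X", with no dose stated. The dose pattern is established only for the immune-complex events.
- That Section 10.5 promises a same-day laboratory change. Its pre-dose to post-dose wording is also used for vital signs and ECGs and can mean baseline against on-treatment visits.

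Two further limits stand. Section 6.5 ties only the synovial sample to the time before injection, so placing the Week 6 count before the dose is a reading of list order. And the added counts cover one of six injections, at a time chosen because a draw already exists.

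**Conclusion.** The point holds in two linked parts. First, the margin statement in Section 2.3.5 does not cover the immune-complex events at 10 and 50 mg/kg, and Sections 2.3.3 and 2.3.5 must be reconciled. This needs no assumption. Second, no scheduled count clearly falls within a week after an injection: the earliest is 8 days at the edge of the windows and nominally 14. A transient, symptomless platelet fall could therefore be missed, while a persistent fall could appear at Weeks 6, 12 or 24.

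The second part assumes that the Week 6 count precedes the injection. It matters most if acute means hours rather than days, which the documents do not state. They also do not show that such events are likely in humans. The gap is modest and cheap to narrow, and it bears on the primary safety endpoint.

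**What to change.** 1. In Section 2.3.5, limit the exposure-margin statement to pharmacology-driven findings, state that it does not extend to the immune-complex events, and cross-refer to Section 2.3.3.
2. Add a platelet count to the Week 10 pre-dose and 2-hour post-dose draws that are already planned. A 2-hour tube at Week 0 is optional: it would pair with the existing Baseline count, but at a first dose it serves only as a control.
3. Reconcile Section 6.7 with Sections 1.3, 4.1 and 9.4 by restoring the pre-dose serum ADA sample to the Week 10 list.
4. In Section 10.5, add a listing of each subject's same-day platelet change beside the ADA result.
5. State in Section 6.5 whether the Week 6 laboratory samples precede the injection.

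Cost: about 24 tubes for 12 subjects (36 with the optional one) at venipunctures already scheduled, a schedule footnote, one listing and a few sentences. The downsides are slightly more blood, coverage of a single injection, and a 2-hour time that may not match the timing of the animal events. This concerns measurement only; it sets no dose or treatment rule.

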#### **2.3.4. Non-Human Primate Intra-articular Administration of AMB-05X**

The clinical formulation of AMB-05X was sequentially injected at two dose levels into the knees of 4 normal male 6-10 kg cynomolgus monkeys (AMB051-20-NHP1 CRL-Reno). On Day 1, anesthetized animals received a dose of 1.5 mg/kg (a human-equivalent dose of ~100 mg), 0.035 mL/kg and a time-course of serum sampling was performed over the following week and the injected knee was sampled for synovial drug levels on Day 8. Three weeks after the first IA administration, the protocol called for injection of the other knee at 5 mg/kg (█ mL/kg of the █/mL AMB-05X formulation), but the animals were inadvertently dosed at ~0.04 mL/kg again and hence, ~2.5 mg/kg or a human equivalent of ~160 mg. Serum sampling was performed at various time points over a two-week period and synovial drug levels were analyzed one- and two-weeks post dosing. Clinical observations and animal mobility were assessed daily and knee range-of-motion testing was performed on both knees (i.e. with and without AMB-05X dosing) was performed on Days 2 and 7 of each dosing cycle. Food consumption and body weights were additionally monitored. Regardless of the administered dose or time point of examination, there were no observations of abnormal behavior, mobility, or altered knee range of motion measurements. AMB-05X drug levels were generally consistent with modeled projections and was generally linear between the two dose levels. For example, at the █ mg/kg IA dose, the serum AMB-05X  $C_{max}$  was █ µg/mL (mean  $\pm$  SD) and declined to █ µg/mL over the week following dosing. Following the second dosing interval (~2.5 mg/kg), two of four animals had serum and synovial drug levels approximately linearly increased from the 1.5 mg/kg dose and 2 had very low synovial and systemic exposures, potentially related to ADA and currently under investigation. Serum  $AUC_{last}$  values averaged █ µg·hr/mL at █ mg/kg and █ µg·hr/mL at █ mg/kg (for the two animals with substantial exposures). The knee synovial fluid AMB-05X concentration 7 days post-dose was █ µg/mL (█ nM) for both dose levels.

#### **2.3.5. Clinical Safety Extrapolation**

The projected human synovial fluid concentrations are projected to be █ µg/mL (█ nM) throughout a 2-week intra-articular dosing regimen of 150 mg (or greater). This synovial concentration is well above a projected effective concentration. From a systemic exposure perspective, as described above, intra-articular dosing of cynomolgus monkey knees at or above the clinical regimen appeared safe and well-tolerated. Importantly and as anticipated, serum

exposures remained very low - significantly below that associated with any transaminase elevations in Amgen's Phase 1/2 monotherapy study in patients with advanced solid tumors ([Papadopoulos, 2017](#)). As reported, no transaminase elevations or other AEs of concern were observed at an exposure of [REDACTED]  $\mu\text{g}\cdot\text{hr}/\text{mL}$  (1.5 mg/kg IV) and limited AST elevation or other AEs were observed at [REDACTED]  $\mu\text{g}\cdot\text{hr}/\text{mL}$  (3 mg/kg IV). Systemic exposures in the 14-week i.v. monkey GLP toxicology wherein findings through 300 mg/kg were related to exaggerated pharmacology far exceeded anticipated systemic exposures in the pending clinical trial. Thus, nonclinical and prior clinical study results support the 12-week intra-articular dosing trial as designed.

## **2.4. Summary of Clinical Data**

### **2.4.1. Clinical Studies of AMB-05X**

Two clinical studies of IV administration of AMB-05X in subjects with advanced solid tumors have been conducted: a first-in-human monotherapy study, and a combination study with pembrolizumab.

Serious adverse events were reported for 11 subjects (44%), adverse events leading to study discontinuation were reported for 4 subjects (16%), and adverse events leading to withdrawal from investigational product were reported for 5 subjects (20%). Fatal adverse events were reported for 3 subjects (12%); the events occurred in the setting of progressive disease and were considered not related to treatment with AMB-05X by the investigators.

Adverse events considered treatment-related by the investigator were reported by 19 subjects (76%). Periorbital edema (without clinical sequelae) was the most common treatment-related adverse event (11 subjects, [44%]), the majority of events resolved and were managed without intervention. Aspartate aminotransferase increased was also a common treatment-related adverse event (7 subjects, [28%]). Seven subjects (28%) had treatment-related adverse events that were  $\geq$  Grade 3 in severity, and one subject (4%) discontinued AMB-05X due to a treatment-related adverse event (the above-mentioned bilateral deafness DLT). There were no treatment-related serious or fatal adverse events.

Macrophages were quantitated on skin biopsies as an indicator of pharmacologic effect. In all subjects in the 10-mg/kg and 20-mg/kg dose groups who had available skin biopsy data, reductions from baseline in macrophages, as indicated by positive staining for CD68 and/or CD163, were observed at week 5.

